
recordings. 3.) All participants who are women of child bearing potential will receive a urine pregnancy dip test. If the test result is positive the subject will not continue participation in this research study. 4.) Collection and review of new medications to include prescription and vitamins / supplements, allergies and vital signs (Temp, HR, Resp, BP), weight, body mass index (BMI) calculation, and adverse event reporting. 5.) Serial Computed Tomography Imaging or MRI scan will be performed. A high resolution Computed Tomography (CT) Scan of the amputation stump will be performed at Presbyterian Hospital and will take approximately 60 minutes. This scan will be pre-procedural and will serve as a baseline. All CT scans will be performed on a 64-slice scanner (LightSpeed, GE Healthcare), using slice thickness of 1.25 mm and pitch of 1.375. kVp, mA, and FOV will be optimized to the subject and body part to be imaged. Soft tissue and bone kernels will be employed. These images will be volumetrically reformatted into coronal and sagittal planes for confirmation of findings. Additionally, surface-rendered volumetric reformats will be created emphasizing both bony structures and soft tissues. In the event that a CT scan is contraindicated or declined by a study participant, MRI will be performed using a 1.5 T MRI scanner (Signa HDx, GE Healthcare). The MR imaging protocols will include coronal and axial planes using T1-weighted spin echo sequences as well as coronal, axial, and sagittal planes using T2-weighted fast spin echo with fat suppression and/or short tau inversion recovery (STIR) sequences. Again, FOV, TR/TE time, acquisition time and other parameters will be optimized to the subject and body part to be imaged. Intravenous contrast will not be administered for either CT or MR imaging. Images will be reviewed by radiology. Volume measurements of the implanted material will be made on all post-procedural CTs or MRIs. These volumetric measurements are expected to be precise to within 5% of the actual volume of material. Trends in volume of tissue will be analyzed over time across the multiple CT or MRI scans. Both linear and volumetric measurements will be used to quantify implanted material. Subjects must remove compression sleeves prior to CT scans. 6.) To further evaluate pre-surgical amputation stump pain, the study coordinator will provide a Pain Assessment form to the participant to complete. This form will document the nature/charter of the discomfort limiting function and or interferes with their ability to use a prosthetic device. The subject will be instructed to document the discomfort to include frequency, location, intensity (1 to 10 scale with 10 as most intense), type of pain (physiological or phantom). It will include self interventions related to pain and use of prosthetic devices. 7.) Psychosocial Assessment: One of the aims of the proposed study is to evaluate pre- and post-operative quality of life and symptoms of psychological distress. This aim will also consider psychosocial factors (pre- and post- surgery) that predict psychological well-being and quality of life outcomes following surgery. The aim is important for identification of psychosocial factors that may play a role in and be critical to enhancing quality of life outcomes from amputation stump surgery. Participants will be asked to complete a psychosocial battery that includes: a) self-report measures of satisfaction with physical appearance, anxiety and depressive symptoms, social functioning and social avoidance and distress and; b) questionnaires that assess significant predictors of quality of life

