
measure physical function and symptoms in people with musculoskeletal disorders of the upper limb. The DASH is estimated to take approximately 10 minutes or less.f. Functional Mobility Assessment (FMA) is a self-report questionnaire to assess perceived user function related to assistive technology use. The FMA is expected to take approximately 10 minutes or less.g. Prosthetic Device Use History: Compliance with prosthesis use affects activities of daily living (ADLs) as well as impacting social interaction. The participant's prosthetic devices (both pre and post procedure) will be evaluated and a history will be obtained from the participant to determine average daily use and related issues/concerns. This questionnaire is estimated to take approximately 30 minutes for the subject to complete.h. Physical Examination: A physical examination will be conducted to evaluate general UE and LE function and specifically the amputation stump. The stump characteristics will be recorded, including measurements, range of motion, strength, skin integrity/areas of pressure, pain and prosthesis/socket interface. This physical examination is anticipated to take approximately 30 minutes to complete. If upon examination, it is determined that the participant is at increased risk for developing pressure ulcers and/or the participant's current wheelchair and seating is not addressing their needs, they will be referred to the UPMC Center for Assistive Technology for a full assistive technology evaluation per routine clinical care.6. CT Scan with 3D renderings or MRI (Visit 4 PO, Visit 5 PO and Visit 6 PO).7. All participants who are women of child bearing potential will receive a urine pregnancy dip test. If the test result is positive the subject will not continue to the CT or MRI scan. (Visit 4 PO, Visit 5 PO and Visit 6 PO)8. Psychosocial assessment (Visit 1 PO, Visit 3 PO, Visit 4 PO, Visit 5 PO and Visit 6 PO)will be conducted satisfaction with surgical outcomes, quality of life and functional outcomes and improvement in self-esteem, psychiatric distress, and psychological coping.9. Structured Clinical Interview for DSM-IV (SCID) (Visit 4, 5, and 6 PO only) to evaluate any change in the presence/absence of psychiatric disorders and will be compared to PGSV1 SCID results. This SCID will take approximately 45-60 minutes of the subject's time to complete.10. 2D Photographs will be collected at each of the post op visits 11. Limb Pain Assessment will be collected at each of the post op visits . 12. Core Needle Biopsy of fat grafting site - POV3 and POV5 only -(this will only be done with subjects where it is determined by the PI that the biopsy will not interfere with the desired outcome of the fat grafting). In subjects where the biopsy is considered to be appropriate, core biopsies will be taken from the area treated with standard fat graft or treated with SVF concentrated fat graft. These samples will be histologically analyzed for differences in vascularity and other evidence of in vivo activity. The samples will be processed within the UPMC system. The research coordinator will provide telephone follow up 48 to 72 hours to the subject post biopsy. This contact is to obtain a subject self report assessment of signs and symptoms of an adverse event post biopsy (i.e., excessive bleeding, redness, extreme tenderness, and potential signs of infection) as a post procedure standard of care safety assessment. Procedures for Study post operative visits #1-12 usually occur on the same day; however, due to coordination of participant's schedules and travel distance the procedures may be performed on different days as long as the completion of the procedures do not exceed a length of 4 days total. In

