2.15.3 Will biological specimens be stored without identifiers or linkage codes? *

[reviewer notes-]

Section 2 - Research Design and Methods

2.16 Will research participants be asked to provide information about their family members or acquaintances?

* No

2.16.1 Describe what information about the third party will be obtained from the participant:

2.16.2 If the information about the third party is of a private nature, can the identity of the third party be readily ascertained or associated with this information?

*

Describe the private information that will be collected and recorded about the third party:

[reviewer notes-]

Section 2 - Research Design and Methods

Section: Section 2 - Research Design and Methods

2.17

What are the main outcome variables that will be evaluated in this study?

Primary outcomes: Improvement of pain at the amputation site, improved ability to tolerate a prosthesis, and generation of a stable volume of adipose tissue at the amputation site (as measured by clinical assessment by rehabilitation sciences and prosthetics team, quality of life measures, and high resolution imaging). This will be compared between the standard fat grafting group (n=15) and the adipose cell enriched fat grafting group (n=15). Secondary outcomes: Local and systemic complications resulting from fat graft procedure (infection, fat necrosis, hematoma, seroma); basic assays of adipose cell behavior to elucidate the functional properties of adipose cells used for grafting, with correlation to outcomes.

2.18

Describe the statistical approaches that will be used to analyze the study data.

* Addressed below:

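### Imaging volume counts all implanted material, and no rule covers fat necrosis or oil cysts; an arm-masked structured read of the planned scans would be a cheap improvement

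*Combined protocol and SAP*

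**What the plan says.** - **Imaging method (2.6, pre-graft visit, item 5).** CT is used, or MRI where CT is contraindicated or declined. On what is measured, item 5 says "Volume measurements of the implanted material will be made on all post-procedural CTs or MRIs". The accuracy claimed for this is "These volumetric measurements are expected to be precise to within 5% of the actual volume of material". Neither modality uses a contrast agent. On reading the scans, item 5 says only "Images will be reviewed by radiology". The findings to be recorded, the reading form and any masking of the reader are not described.
- **Imaging schedule (2.7, item 6).** "CT Scan with 3D renderings or MRI (Visit 4 PO, Visit 5 PO and Visit 6 PO)", that is, months 6, 12 and 24.
- **Outcomes (2.17).** The primary outcomes include "generation of a stable volume of adipose tissue at the amputation site". The secondary outcomes include "Local and systemic complications resulting from fat graft procedure (infection, fat necrosis, hematoma, seroma)".
- **Other wordings of the volume outcome.** 2.18 ties its effect size to soft-tissue volume, Aim 1 in 1.2 speaks of the persistence of new tissue, and the design paragraph of CS2.1 speaks of graft retention.
- **Risks (5.1, fat grafting procedure).** Fat necrosis, described as making the tissue firm, and oil cysts at the graft site are both listed as common risks.
- **Other routes to necrosis.** 2.7 provides an investigator examination with a volume and appearance scale (item 2), adverse event reporting (item 3) and a separate stump examination at POV4, POV5 and POV6 (item 5h). It also provides "Core Needle Biopsy of fat grafting site - POV3 and POV5 only", limited to subjects in whom the PI judges that a biopsy would not harm the result. The stated histology targets are vascularity and in vivo activity. 5.7 undertakes to capture complication data.
- **Masking (2.3).** The trial is described as non-blinded.
- **IDE application (CS10.1).** It is listed as carrying a clinical protocol, which is not part of the published document.

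**The concern.** A cyst or a patch of dead fat takes up space. A reader who follows item 5 literally and measures the implanted material would include it. The resulting retention figure would then be reported against an outcome worded as adipose tissue.

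Fat necrosis is also an outcome in its own right, and how fully it is counted depends on how hard anyone looks. Firm or symptomatic necrosis should come up at examination. Silent necrosis may not, although scans that might show it are being taken anyway.

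At stake are the meaning of the volume outcome in 2.17, the Aim 2 correlations of cell assays with volume retention, and the completeness of the complication count. The rationale in 1.3 is that enrichment helps the graft survive through better vascularisation. A volume that ignores viability could therefore blur the contrast of interest.

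**Working it through.** **1. The plan's own figure for volume.** 2.18 gives 30 patients, alpha 0.05, power 0.80 (the plan's 0.8 is read as power) and a standardised effect of about 0.9. With n per arm = 2(z_alpha + z_power)²/d²:

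- One-sided: 2(1.645 + 0.842)²/0.81 = 15.3, so 16 per arm. Power at 15 per arm is 0.794, which reproduces the plan.
- Two-sided: 2(1.960 + 0.842)²/0.81 = 19.4, so 20 per arm. Power at 15 per arm is 0.693, which does not.

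The unstated sidedness is a separate matter. The figure shows that the stated effect size concerns soft-tissue volume, and the change proposed here does not alter it.

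**2. Measured quantity against named quantity.** Item 5 of 2.6 measures implanted material, 2.17 names adipose tissue and 2.18 names soft tissue. No rule connects the three terms. The stated 5% precision concerns the amount of material, not its viability. It equals 0.05 × 5 = 0.25 mL for a 5 cc fill and 0.05 × 300 = 15 mL for a 300 cc fill (the range in inclusion criterion 10). A volume obtained by subtracting components cannot be expected to be more precise than that.

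**3. Overlap of scans and biopsies.**

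- Post-operative scans: 30 subjects × 3 visits = 90 at most.
- Biopsy visits are POV3 and POV5; scan visits are POV4, POV5 and POV6. Only POV5 is shared.
- Scans that can have same-visit histology: at most 30/90 = 33%. The other 60/90 = 67% cannot. Selection by the PI lowers the first figure further.

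**4. What a count by arm can show with 15 per arm.**

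| Subjects with a finding | Exact 95% CI (Clopper-Pearson) |
|---|---|
| 0/15 | 0 to 21.8% (upper limit 1 − 0.025^(1/15)) |
| 3/15 | 4.3 to 48.1% |

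Two-sided Fisher p for 15 v 15 is 0.224 for 0 v 3, 0.100 for 0 v 4 and 0.042 for 0 v 5. Such counts describe; they are not a basis for a planned test.

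**5. Illustration with assumed shares.** The documents give no share of non-viable graft, so every share here is an assumption. Let measured retention = viable retention + non-viable share of the graft, with viable retention 50% (standard) and 60% (enriched), a true gap of 10 points.

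| Non-viable share, standard / enriched | Measured retention | Measured gap |
|---|---|---|
| 10% / 10% | 60% / 70% | 10 points |
| 15% / 5% | 65% / 65% | 0 points |
| 5% / 15% | 55% / 75% | 20 points |

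Equal shares leave the gap unbiased. Unequal shares can move it either way.

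**The case against.** - **Soft tissue is a legitimate target.** The purpose is padding over bone and nerve trunks, and 1.2, 2.18 and CS2.1 do not insist on adipose tissue. This stands. The mismatch may be one loose word in 2.17, and a reader might wrongly infer from it that total volume is the wrong outcome. It needs an accurate label, not replacement.
- **The scans may not be able to measure necrosis.** No section shows that non-contrast CT or MRI can separate or measure necrotic fat in a scarred stump. This stands. It is why the read should allow a not-assessable answer and why net volume can only be exploratory. The lack of a rule separating graft from native tissue is a further question that this point leaves open.
- **Existing ascertainment is better than it looks.** The stump examination (2.7, item 5h) falls at the same visits as the scans, 5.7 captures complications, and histology of in vivo activity could touch on viability. This largely stands. What remains is silent necrosis, whose frequency and importance the documents do not give.
- **Masking.** A reader might infer from 2.3 that radiology knows the arm. The documents do not say so. The ethics board's remark in CS1.1.1 about unblinded assessment concerned investigators in an earlier, disapproved application. Removing the arm label is a precaution, not the repair of a shown fault.
- **The IDE protocol may already hold a reading rule.** It cannot be checked here.

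**Conclusion.** The point holds as an optional improvement, something the sponsor could do. As item 5 of 2.6 is worded, necrotic fat and oil cysts would count as retained graft. A named secondary outcome also lacks a systematic, masked route through scans that are already planned.

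The size and direction of any effect on the volume comparison cannot be derived from the documents. A reader might infer from step 5 that the comparison is biased towards one arm, or that the retention result is invalid. Neither is supported, because the shares are assumed and equal shares give no bias. Pain and prosthesis use, which 1.2 and 3.12 put first, are not affected.

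The conclusion assumes that no reading rule exists in the IDE protocol and that the scans can show at least some of these findings.

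**What to change.** - **2.6 item 5 and 2.7 item 6:** have the planned radiology review and the volume measurement of the POV4, POV5 and POV6 scans done without the arm label. Record fat necrosis, oil cysts and fluid collections at the graft site as yes, no or not assessable, with the modality.
- **2.17:** report the number of subjects with imaging-detected findings by arm, descriptively, with exact confidence intervals and separately from clinically reported complications. Label the volume outcome total implanted (soft-tissue) volume.
- **Optional:** an exploratory sensitivity analysis of volume net of these components, only where the reader judges them measurable.
- **If the IDE protocol already has such a rule,** cite it in 2.6 instead.

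The cost is extra reading time on at most 90 scans and removal of the arm label from the read request, with no new scan, visit or radiation. The documents do not price the reading time. CT and MRI may differ in what they show, so findings need to be read by modality. Stump scans will not cover seroma at the donor site, which is the only seroma site that 5.1 describes.

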
derived stem cells (ASC) Proliferation: Cellular proliferation of preadipocytes will be assessed with the CyQUANT Cell Proliferation Assay Kit (Invitrogen, Carlsbad, CA) at 48 and 96 hours. Media will be changed every 48 hours. Adipose derived stem cells (ASC) Differentiation: To assess the potential of the ASC to differentiate into the adipogenic cell type within the HA gels, cells will be treated plating media containing 0.2 nM dexamethasone, 0.5 uM insulin, 0.2 nM triiodothyronine, antibiotics, and 540 uM IBMX in addition to their current media. To confirm adipogenesis, lipid inclusions cells will be confirmed by staining with Oil Red-O. Additionally, protein expression of PPAR gamma and FABP4 will be determined using western blot analysis, and RNA expression of these adipogenic markers will be determined using PCR. Flow Cytometry Adipose derived stem cells (ASC) characterization: We will characterize ASC from each patient for stem cell surface antigens using flow cytometry. Passage zero preadipocytes isolated (as described above) from the abdominal subcutaneous tissue will be divided into aliquots of 5x10 (5) cells and stained with selected monoclonal antibodies (mAbs) against progenitor cell surface markers. The antibodies include mAbs against CD34, CD45, CD90, CD133, CD105 and CD166. Rationale for these surface markers includes the following: 1) markers that are routinely examined for bone marrow stem cell markers, and have also been examined as ASC markers and 2) will be able to discern stem cell purity by testing for these markers. The cells will be incubated with mAbs C, and washed in PBS. At least 100,000 viable cells will be incubated for 30 min with 7AAD(-) staining in each sample will be acquired and analyzed using a FACS Aria fluorescence-activated cell sorter (Becton-Dickinson).

2.6.1

Will blood samples be obtained as part of this research study?

* Yes *If submitting a protocol for expedited review, it should be clear that the planned blood draws are within the parameters described here:

<http://www.hhs.gov/ohrp/policy/expedited98.html> (see Expedited Research Category #2)

If Yes, address the frequency, volume per withdrawal, the total volume per visit, and the qualifications of the individual performing the procedure: Lab tests via peripheral blood draw performed by laboratory personnel located on the 5th floor of UPMC MUH building. For blood tests, approximately 30ml (2tbsp) will be collected at the following time points: 1. Screening 2. Preoperative (PGSV)

Study Flow Chart:

| Name | Modified Date |
|---------------------|--------------------|
| AMP 30 Schema MOD 5 | 7/10/2015 10:47 AM |

[reviewer notes-]

Section 2 - Research Design and Methods

- 2.7 Will follow-up procedures be performed specifically for research purposes? Follow-up procedures may include phone calls, interviews, biomedical tests or other monitoring procedures.* Yes

See study flow chart in question 2.6

Post-operative assessments for clinical outcomes of treatment include amputation stump form and pain assessment, evaluation by prosthetics and occupational therapy, nutritional evaluations (baseline, POV1 and POV3 only) and QOL measures will be performed at 7-21 days, 2, 3, 6, 12 months and at 24months after treatment. Patients will be followed for approximately 2 years after surgery; the structure of these visits is outlined below. There are no more follow-up procedures planned or anticipated after post-op visit 6. Post op study visit (Day 3-6): This study visit will occur with the study investigator or research team and will take place approximately in 3-6 days post surgical procedure for the purpose of incision assessment and potential suture removal, if applicable. The entire visit will take approximately 30-45 minutes and will be scheduled with the subject prior to hospital discharge post fat graft procedure. 1. Limited medical history and physical exam with a limb exam completed by the PI and /or the Co-investigator 2. Adverse Event Reporting (Should an adverse medical event occurred prior to the visit and be reported by the subject, the research team will do due diligence to collect information pertaining to the event through subject report and /or medical record review and /or referring physician report) 3. Collection of subject's medication profile to include prescription and vitamins / supplements, allergies, vital signs (Blood Pressure, Heart rate, respirations, temperature) and collection and distribution of Post-operative Diary Card and Pain Log . The subject will be asked to continue logs if an event/issue persists beyond normal post op healing, until the next post-op visit (POV1) POSV1-6 (Post-Operative Study Visits 1-6) The following study visits will occur with the study investigator or research team and will take place at 7-21 days (POV1), month 2 (POV2), month 3 (POV3), month 6 (POV4), month 12 (POV5) and two years (POV6) (+/- 2 weeks) after the surgical fat grafting procedure. The duration of time for each visit will be approximately 3-4 hours. All visits will be scheduled by the research coordinator and discussed with the subject prior to the fat graft procedure. The following research procedures will be completed at this visit: 1. Collection of subject's medication profile to include prescription and vitamins / supplements, allergies, vital signs (Temp, HR, Resp, BP) and weight and BMI calculation and post operative pain assessment 2. Limited medical history & physical exam including amputation stump completed by the PI and /or the Co-investigator. The investigator will rate the appearance/volume of the graft site using the limb volume and appearance grading scale 3. Adverse Event Reporting (Should an adverse medical event occurred prior to the visit and be reported by the subject, the

research team will do due diligence to collect information pertaining to the event through subject report and /or medical record review and /or referring physician report)4.

Nutritional Evaluation (POV1) and (POV3) only: Each subject will recall their dietary intake over the 48 hours prior to the visit date to be evaluated for current nutritional habits.

Nutritional education will be provided by the research coordinator /co-investigator based on the evaluation of the subject's dietary intake record. This education, if necessary will follow Recommended Daily Allowances (RDA) and American Heart Association (AHA) recommendations. Approximate time estimated 20 minutes.5. Prosthetic and Orthotic: At

Visit 2 and/or 3 PO only the subject will be evaluated by the Prosthetic /Orthotics/Occupational therapy team (limited physical exam) in conjunction with the PI to determine weight bearing readiness as well as readiness to obtain a standard of care check socket by their primary prosthetist. The participant's prosthetic device (including check socket and or permanent socket) and any other assistive devices used will be fitted as part of their routine standard of care and will only be documented that the visit happened. The subject will be instructed NOT to wear the prosthetic sockets until seen by research team and/or clearance received to utilize any new prosthetic devices which is anticipated to occur at approximately POV3 or POV4. The subject may be asked to attend an interim visit at 4-5 months PO, if the check socket and permanent socket fabrication fall out of the PO visit 2-3 range. At Post op visit 4 (6 months post op), POV5 (month 12) and POV6 (month 24) the prosthetist and therapist will implement the assessments and select the appropriate assessments based on the participant's functional status, amputation site(s), and assistive technology used. The following assessments are dependent upon the location (upper verses lower extremity) and may or may not be completed depending upon the site of interest. a. Prosthetics Evaluation Questionnaire (PEQ) is a self-report questionnaire containing 54 questions organized into nine functional domains related to prosthesis-related changes in quality of life. The PEQ was developed to fill the need for a comprehensive self-report instrument for individuals with lower limb loss. (Legro 1998). Psychometric analysis supported the reliability and validity of the PEQ for evaluating the function of the prosthesis and the major health related quality of life domains. The PEQ is estimated to take 15 minutes or less to complete. b. The 6 Minute Walk Test (6MWT) is a reliable measure of functional capacity, involves a moderate degree of exercise intensity, and is related to a moderate degree to postural control abilities in persons with lower-limb amputations. (Lin S-J, Bose NH, 2007). This 6MWT is estimated to take 20 minutes or less to complete, including the baseline rest period, set-up, and 6 minutes of continuous walking. This test will not be conducted if the participant is not able to functionally ambulate with use of prosthetic device. c. The Amputee Mobility Predictor (AMP) is a 21 item instrument designed to assess determinants of the lower-limb amputee ability to ambulate. The AMP is estimated to take approximately 15 minutes or less to complete. d. Lower Extremity Functional Scale (LEFS) is a self-reported questionnaire containing 20 questions about a person's ability to perform everyday tasks. The LEFS is anticipated to take approximately 10 minutes or less to complete. e. The Disabilities of the Arm, Shoulder, and Hand (DASH) outcome Measure is a 30-item, self-report questionnaire designed to

measure physical function and symptoms in people with musculoskeletal disorders of the upper limb. The DASH is estimated to take approximately 10 minutes or less.f. Functional Mobility Assessment (FMA) is a self-report questionnaire to assess perceived user function related to assistive technology use. The FMA is expected to take approximately 10 minutes or less.g. Prosthetic Device Use History: Compliance with prosthesis use affects activities of daily living (ADLs) as well as impacting social interaction. The participant's prosthetic devices (both pre and post procedure) will be evaluated and a history will be obtained from the participant to determine average daily use and related issues/concerns. This questionnaire is estimated to take approximately 30 minutes for the subject to complete.h. Physical Examination: A physical examination will be conducted to evaluate general UE and LE function and specifically the amputation stump. The stump characteristics will be recorded, including measurements, range of motion, strength, skin integrity/areas of pressure, pain and prosthesis/socket interface. This physical examination is anticipated to take approximately 30 minutes to complete. If upon examination, it is determined that the participant is at increased risk for developing pressure ulcers and/or the participant's current wheelchair and seating is not addressing their needs, they will be referred to the UPMC Center for Assistive Technology for a full assistive technology evaluation per routine clinical care.6. CT Scan with 3D renderings or MRI (Visit 4 PO, Visit 5 PO and Visit 6 PO).7. All participants who are women of child bearing potential will receive a urine pregnancy dip test. If the test result is positive the subject will not continue to the CT or MRI scan. (Visit 4 PO, Visit 5 PO and Visit 6 PO)8. Psychosocial assessment (Visit 1 PO, Visit 3 PO, Visit 4 PO, Visit 5 PO and Visit 6 PO)will be conducted satisfaction with surgical outcomes, quality of life and functional outcomes and improvement in self-esteem, psychiatric distress, and psychological coping.9. Structured Clinical Interview for DSM-IV (SCID) (Visit 4, 5, and 6 PO only) to evaluate any change in the presence/absence of psychiatric disorders and will be compared to PGSV1 SCID results. This SCID will take approximately 45-60 minutes of the subject's time to complete.10. 2D Photographs will be collected at each of the post op visits 11. Limb Pain Assessment will be collected at each of the post op visits . 12. Core Needle Biopsy of fat grafting site - POV3 and POV5 only -(this will only be done with subjects where it is determined by the PI that the biopsy will not interfere with the desired outcome of the fat grafting). In subjects where the biopsy is considered to be appropriate, core biopsies will be taken from the area treated with standard fat graft or treated with SVF concentrated fat graft. These samples will be histologically analyzed for differences in vascularity and other evidence of in vivo activity. The samples will be processed within the UPMC system. The research coordinator will provide telephone follow up 48 to 72 hours to the subject post biopsy. This contact is to obtain a subject self report assessment of signs and symptoms of an adverse event post biopsy (i.e., excessive bleeding, redness, extreme tenderness, and potential signs of infection) as a post procedure standard of care safety assessment. Procedures for Study post operative visits #1-12 usually occur on the same day; however, due to coordination of participant's schedules and travel distance the procedures may be performed on different days as long as the completion of the procedures do not exceed a length of 4 days total. In

Section: Section 2 - Research Design and Methods

addition, due to the subjects traveling distances who are enrolled into this trial, we have included a (+/-) of 14 days (2 weeks) for the completion of POVisit 1- Visit 6 as a convenience for the coordination of schedules.Upon completion of POSV 6 and pending any adverse event reporting information received, the subject's participation in this study will be concluded. TELEPHONE INTERVIEWS (20-30min; done by coordinator)Telephone Interviews 1 and 2- The phone interviews will consist of a collection of current medications and any concerns or problems experienced after biopsy ((i.e., excessive bleeding, redness, extreme tenderness, and potential signs of infection) as a post procedure standard of care safety assessment. Telephone Interview 3 - (18 months post operative procedure +/- 2 weeks) — This phone interview will consist of a collection of current medications, allergies to update the profiles limb pain subject report assessment including any concerns or problems encountered related to use of a prosthesis .

[reviewer notes-]

Section 2 - Research Design and Methods

2.8 Does this research study involve the use of any questionnaires, interview or survey instruments?* Yes

Upload a copy of all materials except for the SCID or KSADS which are on file at the IRB. The use of all instruments must be addressed in question 2.6 and/or question 2.7 (except for an exempt submission where they should be addressed on the appropriate uploaded exempt form).

| Name | Modified Date |
|---------------------------------|--------------------|
| Diary Card | 7/24/2012 3:06 PM |
| BECK | 2/17/2015 2:05 PM |
| Pain Log | 7/24/2012 3:07 PM |
| QOL Demographics_Brief | 2/17/2015 2:13 PM |
| LEF | 3/31/2014 11:48 AM |
| Prosthetics Usage Questionnaire | 7/24/2012 3:05 PM |
| QOL Demographics | 2/17/2015 2:13 PM |
| SF-36 | 2/17/2015 2:14 PM |

Section: Section 2 - Research Design and Methods

| | |
|---------------------------------------|---------------------|
| SWAP | 2/17/2015 2:08 PM |
| PHQ-Brief | 2/17/2015 2:10 PM |
| ROSENBERG SEI | 2/17/2015 2:11 PM |
| Pain Assessment Tool V 3.0 (10.12.16) | 10/17/2016 12:29 PM |
| PEQ | 7/24/2012 3:03 PM |
| SAD | 2/17/2015 2:09 PM |
| Functional Mobility Assessment | 7/24/2012 3:06 PM |
| Amputee Mobility Assessment | 4/2/2014 1:47 PM |
| AMP | 9/27/2012 1:51 PM |
| COPE | 6/17/2016 9:28 AM |
| CSQ-8 | 2/17/2015 2:09 PM |
| PSSQ | 2/17/2015 2:12 PM |
| DASH | 11/15/2013 11:55 AM |
| PCL-S | 2/17/2015 2:11 PM |

Previously the name and publisher for commercially available materials were listed in the textbox below but effective 9/1/2015, all materials (except for the SCID and KSADS) must be uploaded using the Add button above.

[reviewer notes-]

Section 2 - Research Design and Methods

2.9 If subjects are also patients, will any clinical procedures that are being used for their conventional medical care also be used for research purposes?* yes

If Yes, describe the clinical procedures (and, if applicable, their frequency) that will be used for research purposes: Medical record information that will be extracted from the medical chart review is limited to only those items pertaining to the subject's history of the trauma and all surgical procedures, consults, medications, lab values, and culture results leading up to the fat grafting procedure. Pre-procedure blood tests, including but not limited to blood clotting, red blood cell count, electrolytes, and cultures,

Section: Section 2 - Research Design and Methods

history/physical exams of the body (especially the affected limb), MRI and CT scans, menstrual status and/or results of pregnancy testing, and any medical information that could adversely impact the outcome of the fat grafting procedure. Permission to contact the participant's prosthodontist may be obtained to identify specific prosthetic devices/components previously trialed as part of routine clinical care as well as new prosthetic devices/components received during the course of the subject's participation in this clinical trial.

2.10 The blood sample question was moved to 2.6.1.

[reviewer notes-]

Section 2 - Research Design and Methods

2.11 What is the total duration of the subject's participation in this research study across all visits, including follow-up surveillance?* 26-28 months

[reviewer notes-]

Section 2 - Research Design and Methods

2.12 Does this research study involve any type of planned deception? If Yes, you are required to request an alteration of the informed consent process (question 4.7)

* No

2.12.1 Describe the planned deception:

*

2.12.2 Provide a justification for this planned deception:

*

2.12.3 Describe when and how subjects will be debriefed:

*

[reviewer notes-]

Section 2 - Research Design and Methods

Section: Section 2 - Research Design and Methods

- 2.13 Does this research study involve the use of UPMC/Pitt protected health information that will be de-identified by an IRB approved "honest broker" system?

* No

- 2.13.1 Identify the name of the honest broker system:

- 2.13.2 Specify the IRB-assigned honest broker system number (e.g., HB123456):

- 2.13.3 Specify the names of the individuals who will provide the honest broker services:

| Last | First | Organization |
|------|-------|--------------|
|------|-------|--------------|

There are no items to display

Previous inputted information for Question 2.13.3:

- 2.13.4 Upload the signed honest broker assurance agreement:

| Name | Modified Date |
|------|---------------|
|------|---------------|

There are no items to display

[reviewer notes-]

Section 2 - Research Design and Methods

- 2.14 Will protected health information from a UPMC/Pitt HIPAA covered entity be accessed for research purposes or will research data be placed in the UPMC/Pitt medical record?* Yes

If you answer Yes, you are required to submit this study to the Research Informatics Office, Health Record Research Request (R3). Per UPMC Policy HS-RS0005, all research projects that access or involve UPMC electronic protected health information (e-PHI) must be submitted to R3, with the exception of clinical trials that are contracted through the UPMC Office of Sponsored Programs and Research Support (OSPARS). Complete the R3 intake form available at <http://rio.pitt.edu/services>. An R3 representative will conduct a review. You will be notified once your R3 review is complete or if anything further is needed.

Describe the medical record information that will be collected from the UPMC/Pitt HIPAA covered entity and/or the research-derived information that will be placed in the medical records. The medical record information that will be extracted from the medical chart review are only those items pertaining to the subject's history of the trauma and all surgical

